## **5.0 Study Design and Methods**

### **5.1 Description of Study Population and Recruitment**

This is a pilot single site study and participants will be enrolled at the NIH Clinical Center. Recruitment will occur from a pool of normal volunteers, individuals with known SCT or SCD, and patients with SCD who have successfully undergone curative hematopoietic stem cell transplant. Volunteers will be recruited through the Clinical Center Volunteer Office.

The recruitment ceiling is an N=40 to account for screen failures. Accrual will be stopped once the numbers of active participants who have completed data collection have been reached:

- Normal Volunteers: N=3
- Individuals with SCT: N=6
- Individuals with SCD pre-transplantation: N=6
- Individuals with SCD post-transplantation: N=6-10

Accrual will be based solely upon protocol entry criteria and no selection will be based upon gender, race, or age (in those 18 years or greater in age). The study will be listed on the clinicaltrials.gov, Clinical Center research studies, and the National Heart, Lung and Blood Institute patient recruitment websites.

## 5.2 Study Design

[figure not shown]

Figure 1. Schematic diagram of the study design

\*Participants with SCD pre-HSCT will have samples collected weekly until completion of study.

## 6.0 Procedures, Blood Collection, Laboratory Tests and Processing

**6.1 Screening:** Potential and enrolled participants may have had pre-study evaluation procedures conducted for clinical and research purposes under the IRB-approved NHLBI screening protocol 97H0041. Prior, concurrent and subsequent results from pre-study evaluation procedures performed under this screening protocol may be utilized to determine eligibility for this protocol.

If previous pre-study evaluations are not available from 97H0041, then all screening activities will be conducted under this protocol.

First, all volunteers will be evaluated with a medical history and a physical examination. Next, the volunteer will undergo a venous assessment in the Department of Transfusion Medicine (DTM) on the day of screening. Approximately, 50 mL of venous blood will be required for screening. Baseline laboratory tests, including complete blood count (CBC) and differential, reticulocyte count, hemoglobin electrophoresis, type and screen, acute care panel, mineral panel, hepatic panel, markers of hemolysis (DAT, LDH, AST, ALT, and bilirubin), DTM viral screen, existence of pre-existing antibodies to biotin, urinalysis, and a complete medical history will be performed (Table 2). All patients who have received a transplant on a Gene Therapy protocol

may require additional confirmatory HIV testing which will also be performed under this protocol.

Participants with naturally occurring antibodies against BioRBCs will be excluded. All female volunteers of childbearing age will be required to undergo a serum pregnancy test. The screening visit will be used to determine initial eligibility for the protocol. Final subject eligibility will be confirmed once all lab results are noted in CRIS and eligibility criteria are met.

Once eligibility is confirmed, the participant will be scheduled for biotinylation of patient RBCs, and will have  $\alpha$ -Globin genotype determined by Southern blot hybridization of genomic DNA extracted from peripheral blood leukocytes if the genotype is not already known.

**Screen Failures:** If a subject is found ineligible during the screening process and the subject will not meet the requirements within 30 days of the screening visit, the subject will be counted as a screen failure and removed from study.

The subject may re-screen if/when it is believed eligibility criteria may be met in accordance with the PI's discretion. Subjects will need to repeat the DTM viral screen during re-screening, as these lab results are no longer valid after 30 days. Any other test(s) or procedure(s) whose prior result rendered the subject ineligible needs to be repeated to see if more recent results would allow the subject to meet eligibility criteria. A new subject number will be assigned to a subject who is re-screened.

- 6.2 **Biotinylation General:** Collection of RBCs (as per section 6.3), biotinylation of patient RBCs, and re-infusion back to the patient within 48 hours as an outpatient. In the event the collection of RBCs occurs late in the day and biotinylation is unable to be performed the same day, RBCs will be stored overnight at 2-8°C. Biotinylation will be performed at room temperature under sterile conditions by the DTM. The goal total time during which the BioRBCs are at room temperature (i.e. during biotinylation and the transfusion procedure) should not exceed 4 hours. If immediate transfusion is not possible, the BioRBCs should be kept in a monitored refrigerator set at 4°C (range, 1-6°C).
- 6.3 **Collection:** On the day of blood collection, approximately 100 mL of venous blood will be collected via venipuncture for biotinylation of RBCs (~80 +/- 5mL ), routine labs and alpha-Globin genotype (~20 mL). Alpha-Globin genotype will be determined by Southern blot hybridization of genomic DNA extracted from peripheral blood leukocytes if genotype is not already known. For participants without central venous access, an 18- or 20-gauge catheter will be placed in an adequate patient vein. Routine labs include approximately 20 mL of venous blood to provide a baseline complete blood count, reticulocyte count, DAT, and repeat pregnancy test (females only). In addition, whole blood is submitted for the purpose of DTM storage and will be held per DTM policies. DTM isolation procedures as defined in BB-DMF 11054 will be followed. The remaining approximately 70mL of whole blood will be collected in ACDA (Baxter healthcare Corp, Deerfield, IL) to obtain >15mL of packed RBCs (pRBCs). After verification that the DAT is negative, biotinylation of the collected sample may proceed.
- 6.4 **Pre-Biotinylation Washing:** The whole blood product will be visually inspected carefully; if clots/clumps are observed, product will be filtered before further processing. Blood will be centrifuged at 1000 x g (2142 rpm), deceleration (DEC) 4 at room temperature (RT; 17°C –25°C) for 10 minutes in table top centrifuge. The plasma layer will be aspirated and saved for use in reconstituting RBCs after biotin labeling. RBCs will be washed three times with 4 vol (4:1 wash:

RBCs) of PlasmaLyte A (Baxter healthcare Corp, Deerfield, IL). Washed RBCs will be resuspended in sufficient wash buffer to yield a 25% suspension of RBCs.

6.5 **Preparation of Biotin:** The CC-TAG-Biotin (ChemConnection BV, Netherlands) is stored in a -20°C freezer and should be allowed to come to room temperature (~10-15min) before opening of the vial to avoid saturation of the biotin reagent. To prevent hydrolysis of the biotin reagent before addition to the RBCs, the biotinylation reagent will be prepared in wash buffer before use (within 20 minutes). A solution containing 1 mg/ml biotin will be prepared by dissolving 1 mg biotin in 1 mL PlasmaLyte A. This solution will then be sterilized by filtration through a 0.22- $\mu$ m syringe filter (21062-25; Corning Glassware, Corning, NY).

6.6 **Biotinylation Reaction:** Biotinylation will be performed under a sterile Class 2 laminar flow hood in DTM. The appropriate volume of biotin solution will be added with gentle agitation to the 25% RBC suspension to give the desired final concentration of biotin of 18  $\mu$ g/mL, incubated at room temperature for 30 minutes (Preclinical data shows efficiency of biotinylation of sickle RBCs from 1-80  $\mu$ g/mL, however RBC morphology becomes deformed at concentrations >54  $\mu$ g/mL. Flow cytometry peaks separating biotin labeled RBCs from unstained control is best at 18  $\mu$ g/mL compared to lower biotin concentrations, without any evidence of RBC morphology changes at 18  $\mu$ g/mL). The reaction will be terminated by sedimentation of RBCs at 1000 g (2142 rpm), deceleration (DEC) 4 at RT for 10 minutes followed by three 4:1 (vol/vol) buffer washes with PlasmaLyte A, sedimentation, and resuspension; this removes the remaining biotinylation reagent as well as any reaction and hydrolysis byproducts. The washed BioRBCs will be passed through an 18um filter (Hemo-Nate Syringe Filter, Utah Medical Products, Inc, Midvale, UT) and resuspended in autologous plasma at a hematocrit (Hct) of 50% (range 40-60%). 150  $\mu$ L (range 50-500  $\mu$ L) of pre-biotinylated RBCs and 150  $\mu$ L of post-biotinylated RBCs will be withheld and sent to the [name] laboratory for pre-clinical studies (to ensure all cells are labeled and that there is a baseline separation of labeled and unlabeled cells on flow cytometric histogram) via methodology described below (see section 7.1).

6.7 **Final Product:** Final samples are removed for CBC, biotin labelling efficiency determination via flow cytometry, and safety assays (sterility and endotoxin). Release of the drug product is contingent on meeting the criteria listed in the table below (Table 1), which are also listed in the Certificate of Analysis in Module 3.2.P.5.4. For Safety testing, the final drug product must have an endotoxin level of  $\leq$  5 EU/mL and be negative for contamination in the sterility tests. Since the product is infused fresh, release for use is based on gram stain for sterility, with post-infusion testing based on a 14 day culture. The percent hematocrit and the percent of biotinylated RBC's will serve as a measure of purity and identity of the product.

**Table 1: Drug Product Release Criteria**

bioRBC Drug Product Release Testing	Assay type	Method	Acceptable Limit
Purity	Appearance	Visual check	Red; no clots or aggregates
Identity/Purity	% HCT	Advia CBC	$50 \pm 10\%$
Identity/Purity	% Biotinylated RBC	Flow	$\geq 80\%$
Safety	Endotoxin	Limulus amebocyte lysate (LAL)	$\leq 5$ EU/mL

Safety	Sterility	Gram stain	No organisms seen
Safety	Sterility*	Bacterial, BacT/ALERT bacteria culture*	No growth in 14 days*
Safety	Sterility*	Fungal culture *	No growth in 14 days*

\*Pending at release

6.8 **Infusion of Product:** For participants without central venous access, an 18- or 20-gauge catheter will be placed in an adequate patient vein for infusion of biotinylated RBCs (max volume 50 mL) and for obtaining immediate post-transfusion blood samples. Biotinylated RBCs will be reinfused per Nursing SOP for Cellular Therapy Products Administration; the time 20 minutes after the end of the infusion will be designated time zero (time for equilibration). The catheter will be flushed with 5mL normal saline at completion of the infusion. The time zero research lab can be drawn from the same IV in which biotinylated RBCs were infused.

6.9 **Sample Collection:** Study design, assessment parameters, and sample collection intervals (with approximate volume of blood required) are shown in Figure 1, Table 2, and Table 3, respectively. Approximately 5 mL of venous blood will be collected at 20 minutes after infusion for all participants, then approximately 10 mL will be collected at intervals as specified in Table 3 (+/- 3 days); non-transplant SCD participants will have samples collected bi-weekly for the first two weeks, then weekly until the percentage of biotinylated RBCs has decreased to the lower limit of detection (approximately less than 0.06%; estimate 1-8 weeks); all other participants (SCD post-transplant, sickle cell trait, healthy volunteers) will have samples drawn weekly for the first 4 weeks (starting week 2 through week 4) then every other week until the percentage of biotinylated RBCs has decreased to the lower limit of detection (approximately less than 0.06%; estimate 12-16 weeks) (Table 3). All participants will return for anti-biotin antibody detection at 6 months post-infusion (end of study). Samples will be analyzed as described below (sections 7.1-7.5) for % survival biotinylated RBCs, hemoglobin content, F cell percentage, and delay time analysis, with the remainder of the sample sent to the clinical lab, DTM, and the [name] lab for determination of Hb, Hct, reticulocyte count, LDH, AST, ALT, bilirubin, DAT, and detection of antibodies to biotinylated RBCs (see section 6.10)(Table 2). At every encounter, participants will be asked about any illness since their last visit.

**Table 2 Assessment Parameters**

Visit	Parameter	Additional History
Screening	CBC Reticulocyte count Hemoglobin electrophoresis Acute Care Panel Mineral Panel Hepatic Panel DAT ABO/Rh and antibody screen LDH Biotin antibody screen* Serum pregnancy test (females)  **HIV-1/HCV/HBV (NAT) Hepatitis B (surface antigen) Hepatitis B (core antibody) Hepatitis C (antibody)	Complete history including past medical history, transfusion history, bleeding history, and medications. A complete SCD history (where applicable) will include hydroxyurea use and dose, pain crisis frequency, ER and hospitalization utilization, and transfusion history.

	HTLV I and II (antibody) **HIV 1 and 2 (antibody) West Nile Virus T cruzi (antibody) Treponema pallidum (antibody) or equivalent (such as RPR) Urinalysis	
Week 1/Day -1 (Blood Collection)	CBC Reticulocyte count DAT Serum pregnancy test (females) α-Globin genotype  Infectious screening of whole blood per DTM (see 6.3)	Interim illness update (specifically for SCD patients, history of pain crisis, transfusion, ER visit, or recent hospitalization)
Week 1, Day 1 (Infusion Day)	For [name] Lab& bluebird bio  % survival biotinylated RBCs Hemoglobin content F cell percentage Delay time analysis HbF staining HbS single cell Western Blot Assay development	
Study Assessments (Time Zero – End of Study*)	Clinical Lab & DTM [name] & [name] Labs, bluebird bio  CBC Reticulocyte count Acute Care Panel Mineral Panel Hepatic Panel LDH DAT ABO/Rh and antibody screen Hemoglobin electrophoresis Biotin Antibody Detection*	% survival biotinylated RBCs Hemoglobin content F cell percentage Delay time analysis HbF staining HbS single cell Western Blot Assay development  Interim illness update as above

\*Biotin antibody detection will be done at initial screen, during the course of the study if bioRBC degradation is faster than predicted, and at 3 and 6 months post-infusion for all patients regardless of end of study date.

\*\*Gene Therapy patients may have other HIV testing, including HIV ½ Antibody/Ag Combo.

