## 1.0 Introduction and Background

Sickle cell disease (SCD) is a severe hereditary form of anemia in which a mutated form of the beta globin gene distorts red blood cells and decreases red cell survival. Unstable sickle hemoglobin rapidly polymerizes into gelled, aggregated hemoglobin S (HbS) tetramers at low oxygen levels, leading to increased red cell rigidity, oxidative damage of the red cell membrane, distorted red cell morphology, and a shortened red blood cell (RBC) survival. The altered rheology of erythrocytes and chronic hemolysis leads to the numerous downstream effects including activation of monocytes, leukocytes, platelets, plasma proteins and endothelium. This red cell rigidity and subsequent inflammation is responsible for the devastating clinical manifestations of SCD including chronic anemia, viscosity changes, intravascular sludging, stroke, end organ damage, and ultimately, decreased overall survival (1).

Inherent instability of the HbS polymer leads to oxidative damage of the red cell membrane, with subsequent activation of ion channels leading to a dehydrated and acidotic RBC with increased risk for hemolysis and decreased lifespan. In contrast with the lifespan of RBCs from healthy donors (HD) or even individuals with sickle cell trait (SCT) who have been shown to have an RBC lifespan of approximately 107-115 days (2-4), the mean life span of RBCs in patients with SCD is approximately 10-32 days (2, 5-6). Certain molecular factors are thought to affect the severity of anemia in patients with SCD, likely reflected by different rates of hemolysis and therefore different hemoglobin levels at steady state. Several biochemical markers of hemolysis have a correlation to erythrocyte survival in patients with SCD, including a strong inverse correlation with absolute reticulocyte count (ARC) ( $r=-0.84$ ,  $p<0.0001$ ), percent of reticulocytes ( $r=-0.78$ ,  $p=0.002$ ),  $\alpha$  globin gene number ( $r=-0.15$ ,  $p=0.008$ ), and a positive correlation with percent fetal hemoglobin (HbF) ( $r=0.58$ ,  $p=0.038$ ) (2,4). The range of HbF content in fetal hemoglobin containing cells (F cells) appears to be important, with cells on the high end of the range surviving longer than those on the low end (7). Furthermore, the survival of non-F cells correlates inversely with the fraction of F cells, with shorter non-F cell RBC lifespan in patients with a high percentage of F cells independent of hydroxyurea therapy (7).

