**Table 3. Sample Collection Intervals**

		Week 1/Day 0, Infusion Day		Week ^																		
	Screening	Pre-infusion	Post-infusion	1	2	2*	3	4	5	6	7	8	9	10	11	12	13	14	15	16	24	
SCD Pre-Transplantation	X	X	X	X	X	X	X	X	X	X	X	X	X	X	X	X	X	X	X	X	X	
SCD Post-Transplantation	X	X	X		X		X	X		X		X		X		X		X		X		X
HbAS	X	X	X		X		X	X		X		X		X		X		X		X		X
HbAA	X	X	X		X		X	X		X		X		X		X		X		X		X
Approximate Volume of Blood (mL)	50	100	5	10 (per sample collected)																		

^All patients will follow the sample interval until the percentage of biotinylated RBCs has decreased to the lower limit of detection (approximately <0.06%), at which time the next interval for that patient will be the final 6 month (week 24) interval.

2\* = Bi-week 2

**6.10 Antibody Detection:** To test for antibodies to biotinylated RBCs, plasma samples will be tested using gel card antibody detection(MTS anti-IgG Card, MTS084024, Ortho Clinical Diagnostics) as previously described (11). The detection of specific antibodies to bioRBC does not determine whether these antibodies are physiologically active or are clinically significant. Thus far, all identified pre-existing, naturally occurring anti-bioRBC antibodies are neutralized by biotin compounds, while induced anti-bioRBC antibodies are expected to be inhibited by bioRBC and not by free biotin as previously published (11). It is speculated that this is analogous to penicillin-type drug-dependent antibodies with biotin covalently attached to RBC surface proteins acting as immunogenicity enhancing haptens. In those reported cases of anti-bioRBC antibody detection, biotinylation occurred at higher concentrations (54-162 µg/mL), antibodies were transient and no longer detected after 6 months, and did not alter the red cell survival (4,11).

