### **13.8 Assessment of Potential Risks and Benefits**

Risks involved in participation in this study are low and include risks related to blood draws, risks related to protection of confidentiality, and risks related to biotin (see section 12.6). We do not expect to see side effects related to biotinylation of RBCs, however the theoretical safety issue of development of anti-BioRBCs after BioRBC exposure is addressed by screening before, during, and after completion of the study for anti-BioRBCs. Previous studies that have detected BioRBC-induced anti-BioRBC describe

these antibodies as transient with no clinical changes presumably because the volumes of BioRBCs transfused for RBC kinetic studies are small (approximately 0.40 mL of BioRBC/kg body weight) and unlikely to cause a clinically significant transfusion reaction, even if the entire BioRBC transfusion was acutely hemolyzed (4,11). The knowledge gained from this study including RBC survival in patients with SCD before and after BMT, and RBC survival in subjects with SCT (not previously done with biotinylation), will provide essential information that will inform future gene therapy studies while exposing participants to minimal risk.

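### In the pre-transplant SCD cohort no fixed anti-BioRBC test clearly falls while labelled cells circulate, and the conditional test depends on an undefined fast-loss trigger

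*Combined protocol and SAP*

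**What the plan says.** - **Purpose.** The Synopsis lists antibody detection as a secondary endpoint. Section 13.8 (Assessment of Potential Risks and Benefits) says the theoretical risk of induced antibodies "is addressed by screening before, during, and after completion of the study for anti-BioRBCs".
- **Table 2 footnote.** After the screening test, one further test is conditional: it is done "during the course of the study if bioRBC degradation is faster than predicted". The same sentence also fixes two unconditional tests for every participant, the first 3 months and the second 6 months after infusion, whatever the end-of-study date.
- **Section 6.9.** Tests on the post-infusion samples include "DAT, and detection of antibodies to biotinylated RBCs (see section 6.10)(Table 2"). The section then names a return visit for antibody detection at 6 months only. It expects label to reach the detection limit (about 0.06%) in 1-8 weeks in non-transplant SCD and in 12-16 weeks in the other three cohorts.
- **Table 3 footnote.** Once label reaches the limit, the participant's next visit is week 24.
- **Section 6.10.** In reported cases, "antibodies were transient and no longer detected after 6 months, and did not alter the red cell survival". Those cases used 54-162 µg/mL biotin; section 6.6 specifies 18 µg/mL.
- **Section 1.0.** "the mean life span of RBCs in patients with SCD is approximately 10-32 days", against 107-115 days for healthy donors and sickle cell trait. Section 13.4 notes that data on these antibodies are limited in SCD.

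**The concern.** Before 3 months, the Table 2 footnote lets the rate of label loss decide who is tested. That rate is the primary endpoint. In pre-transplant SCD the label is expected to be gone before 3 months, so the conditional test may be the only specific antibody test done while the curve is being measured.

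Three things are at stake in that cohort:

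- A transient antibody that leaves survival unchanged would not fire the trigger. It could be missed altogether if the next test is at week 24.
- An antibody that shortens survival within the stated SCD range would be recorded as ordinary sickle survival.
- If only apparent fast decliners are tested on the curve, antibody can look associated with short survival merely because of who was tested.

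With six participants a single case matters. If one lifespan were halved from 32 to 16 days, the cohort mean would fall by 16/6 = 2.7 days.

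**Working it through.** **Inputs.** Lifespans L of 10-32 days (SCD) and 107-115 days (healthy, trait) come from section 1.0. Label periods and the 0.06% limit come from section 6.9. The documents do not give the labelled percentage at time zero, f0, so 0.5%-2% is assumed. Three months is taken as day 84-91.

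**Model.** A label on cells of all ages declines roughly linearly: fraction left = max(0, 1 − t/L), and time to the limit = L × (1 − 0.06/f0). Exponential decline, exp(−t/L), is the sensitivity case.

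**Step 1: reproduce the plan's label periods.**
- SCD: 10 × (1 − 0.06/0.5) = 8.8 days (1.3 weeks), up to 32 × (1 − 0.06/2) = 31.0 days (4.4 weeks). This lies inside the stated 1-8 weeks.
- Healthy and trait: 107 × (1 − 0.06/0.5) = 94.2 days (13.5 weeks), up to 115 × (1 − 0.06/2) = 111.6 days (15.9 weeks). This lies inside the stated 12-16 weeks.

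**Step 2: does the 3-month test fall while label circulates?**
- L = 107-115 days: 1 − 91/107 = 15% to 1 − 84/115 = 27% of labelled cells remain. Multiplied by f0, that is 0.075%-0.54% of red cells, above the limit throughout. Section 6.9 gives post-transplant participants the same 12-16 weeks.
- Pre-transplant SCD: 0% remains under linear decline. The plan's own upper estimate, 8 weeks, is day 56, before day 84.
- Sensitivity: with exponential decline and L = 32 days, the limit is reached at 9.7-16.0 weeks, longer than the plan's estimate, so a long-lived participant might still carry label at 3 months. With L = 10 days it is reached at 3.0-5.0 weeks.

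**Step 3: can the trigger discriminate in SCD?** Percentage of label left, with L = 16 representing a halved 32-day lifespan:

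| Day | Decline | L = 10 | L = 16 | L = 32 |
|---|---|---|---|---|
| 7 | linear | 30% | 56% | 78% |
| 7 | exponential | 50% | 65% | 80% |
| 14 | linear | 0% | 12.5% | 56% |
| 14 | exponential | 25% | 42% | 65% |

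The halved lifespan sits inside the expected range on both days and under both shapes.

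**Step 4: the same question in healthy and trait participants.** At day 28, 1 − 28/107 = 73.8% to 1 − 28/115 = 75.7% is expected. A lifespan halved from 115 to 57.5 days leaves 1 − 28/57.5 = 51.3%, clearly outside. There the trigger could work once a threshold is set.

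**Step 5: the passages on the 3-month test.** The Table 2 footnote promises it to everyone regardless of end-of-study date. The Table 3 footnote gives a cleared participant no visit before week 24, and section 6.9 names 6 months only. A pre-transplant participant cleared by week 8 therefore has a 3-month test in one place and no visit for it in the other two.

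**The case against.** Several stronger conclusions are tempting, and the documents do not support them.

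- *The conditional test is the only one while labelled cells circulate.* This is wrong for three of four cohorts. The 3-month test is unconditional and falls in their 12-16 week label period, so positives with normal survival are not simply left uncounted there.
- *The trigger cannot find the risk.* This is too strong. Sections 13.6 and 13.8 discuss hemolysis of the infused cells, which would show as faster loss. Step 4 shows that a defined trigger could detect that where the expected range is narrow. An antibody that does not alter survival also does not bias the lifespan estimate; missing it harms the secondary endpoint.
- *A fall from 32 to 10 days (22/32 = 69%) would pass unnoticed.* This holds only if prediction means the 10-32 day range. The Synopsis gives about 32 days for SCD, and against that figure 10 days is fast. Sections 3.0 and 7.7 tie lifespan to the reticulocyte fraction, which might allow individual predictions. The documents do not say which prediction applies.
- *None of the six will be tested on the curve.* This cannot be verified. Section 6.9 could mean every interval sample is tested, although its reference to Table 2 may import the footnote's conditions. Both appendices have a biotin antibody row, but its visit shading cannot be read in the text available.
- *The repeated DAT is worthless because few cells carry label.* The labelled fraction and the DAT's sensitivity at that fraction are not documented. Table 2 does list "LDH DAT ABO/Rh and antibody screen Hemoglobin electrophoresis Biotin Antibody Detection" for study assessments; the biotin assay is a separate entry, so the DAT is not shown to replace it.

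It is also fair that this is a descriptive pilot, that 18 µg/mL may lower the antibody rate by an unquantified amount, and that no antibody onset time is given.

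**Conclusion.** The concern holds for the pre-transplant SCD cohort, N=6. On the plan's own 1-8 week estimate, no fixed post-infusion antibody test clearly falls while label circulates. The 3-month test is contradicted by the Table 3 footnote and omitted from section 6.9. The conditional test has no threshold, depends on the primary endpoint, is uninformative if judged against 10-32 days, and would miss antibodies of the kind section 6.10 describes. Unless section 6.9 means testing at every interval, the *during* part of the screening claimed in section 13.8 is not secured for this cohort.

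The gap is smaller in the other three cohorts because of the unconditional 3-month test.

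The timing conclusion rests on section 6.9's label estimates. The percentages rest on linear decline, with exponential decline as a check. The exact number of scheduled tests is not verifiable. This should be fixed, but it does not undermine the design as a whole.

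**What to change.** 1. Add one fixed anti-BioRBC test on plasma already drawn at week 4, which Table 3 samples in all four cohorts, or on the last survival sample if label clears sooner. Do this at minimum in pre-transplant SCD and preferably in everyone. Since a sample is known to be the last only after its flow result, keep a plasma aliquot from each earlier interval sample.
2. Keep the fast-loss test only as an addition, and define its reference curve, time point and threshold.
3. Keep the 3-month test for participants whose label has cleared. A very early last sample may precede antibody formation.
4. Report mean potential lifespan with and without antibody-positive participants.
5. Reconcile section 6.9, the Table 2 and Table 3 footnotes, section 13.8 and both appendices, stating whether each interval sample is tested and whether the 3-month test stands.

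**Cost.** About 6 gel-card tests, or 3 + 6 + 6 + (6 to 10) = 21-25 if all cohorts are included, plus a protocol amendment. The added test needs no extra visit or draw. The 3-month visit for cleared participants is one that Table 2 already calls for and Table 3 leaves out. Week 4 is a practical choice, since the documents give no onset time.
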